#### 4.2. Outcome

The main outcome measure is an improvement in the validated Voice Handicap Index self-assessment score following up to six sessions of therapy by an authorised CVT-P in patients with MTD ([Appendix 1](#))

Secondary outcome measures include:

- 1) A questionnaire to evaluate the acceptability of the approach to patients ([Appendix 2](#))
- 2) A questionnaire to evaluate the perceived effectiveness of the therapy from the Therapist's perspective. ([Appendix 3](#))
- 3) Qualitative comparison of the specific techniques used by the CVT-P based on a log of techniques used during the therapy session ([Appendix 4](#)) and qualitative assessment of anonymised, redacted transcripts of therapy sessions in those who have given additional consent
- 4) Comparison of pre- and post-treatment results of:
  - a. a range of simultaneously acquired acoustic and EGG measures made on voice recordings of continuous speech, phrases based on phonetically selected texts and sustained vowels ([Appendix B](#))

- b. psychoacoustic evaluation of the recorded voice samples using the CAPE-V ([Appendix 5](#)) and CVT derived assessment tools ([Appendix 6](#))
  - c. vocal tract discomfort scale – a self-reported rating scale ([Appendix 7](#))
  - d. change in the aerodynamic measure, the Maximum Phonation Time (MPT) ([Appendix 8](#))
- 5) Review of qualitative and quantitative results with recommendations on the feasibility and design of performing a larger RCT. The results will be published in a peer reviewed publication

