### Acoustic, EGG and MPT measures

Paired-samples t tests will also be applied to the secondary acoustic outcome measures (EGG, acoustic and MPT measures), together with 95% confidence intervals.

To control for Type 1 error of the primary outcome and secondary outcome analyses while maintaining an acceptable level of statistical power, the alpha level for all t-test comparisons will also be assessed at .025. Treatment effects will be assessed by comparing the pre-treatment to post-treatment change ( $\Delta$ ) scores, plotted as a forest plot in order to display the average  $\Delta$  change for each outcome measure and corresponding 95% confidence interval. Any significant treatment effects will be followed up with calculations of effect size using Cohen's d.

SHORT TITLE/ACRONYM: CVT4MTD

IRAS:306954

Measurement reliability for acoustic analyses will be calculated by reanalysis of 10% of the recordings. The recordings chosen for reliability analysis will be randomly selected from the total number of recordings. Pearson product–moment correlations will be used to assess inter-measurer and intra-measurer reliability of the acoustic and EGG measurements.

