### **CAPE-V**

For the secondary outcome measure CAPE-V, three experienced judges will be asked to rate all voice samples using the first four dimensions (overall severity, roughness, breathiness, and strain; on 100-mm visual analog scales (VAS) (Kempster et al, 2009). The judges will be blinded to pre- and post-treatment status of the voice samples. The voice samples will be presented in random order. The rating forms will be scored, and then scores for each subject will be averaged across the three judges. Average scores will be used for group analyses. Interrater agreement will be assessed using procedures described by Kreiman and Gerratt (1998). Agreement equivalent to within 1 point on a 7-point Equal Appearing Interval (EAI) scale will be calculated for each possible pair of raters for each voice sample. On a 100-mm visual analog scale, scores that fall within 7.2 mm will be considered to be in exact agreement on a 7-point EAI, and scores that are within 21.5 mm (7.2 + 14.3 mm) will be considered to be within 1 scale value. Two scores will be considered to agree if they fall within  $\pm 21.5$  mm on the VAS (probability of chance agreement  $p = 0.39$ ). The probability of agreement will be calculated by totaling all pairs of scores that agree and dividing by the total number of score pairs. Twenty percent of the voice samples will be randomly selected to be repeated for each judge. Repeat ratings will be used to assess intra-rater agreement, using the same calculation. To test for differences in the four CAPE-V dimensions, a multivariate analysis of variance will be applied to the pre-treatment to post-treatment change ( $\Delta$ ). Paired-samples  $t$  tests will also be applied to pre-treatment to post-treatment changes for each of the four dimensions within each group. A multiple comparison adjustment will be made for the four comparisons using the Bonferroni multiple-comparison procedure. The confidence intervals will be similarly adjusted for four comparisons, so the reported 95% confidence interval (CI) will actually be a 98.75% CI, which is a Bonferroni-adjusted CI.

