## 7. SAMPLE AND RECRUITMENT

### 7.1. Eligibility Criteria

All patients who meet the inclusion/exclusion criteria and who give consent will be invited to take part. Ten consecutive patients will be recruited. All participants will have a multidisciplinary and multidimensional assessment (see Table 2) and considered for the study if they have a clinical diagnosis of Type I-III MTD based on consensus agreement of the patient by an SLT-V and

SHORT TITLE/ACRONYM: CVT4MTD

IRAS:306954

Laryngologist and meet the study criteria. No participants will be excluded based on race, ethnicity, or gender.

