## 10. APPENDICES

### 10.1. Appendices 1- Required documentation

19ET004 **Appendix 1** VHI -Voice Handicap Index V1.0 12 Jan 2022

19ET004 **Appendix 2** Achievement of goals Patient feedback questionnaire V1.0 12 Jan 2022

19ET004 **Appendix 3** Achievement of goals Therapist feedback questionnaire V1.1 21 Mar 2022

19ET004 **Appendix 4** Log of Therapist Treatment in session V1.0 12 Jan 2022

19ET004 **Appendix 5** CAPE-V rating form V1.0 12 Jan 2022

19ET004 **Appendix 6** CVT Speech Assessment V1.0 12 Jan 2022

19ET004 **Appendix 7** Vocal tract Discomfort scale V1.0 12 Jan 2022

19ET004 **Appendix 8** Maximum Phonation Time V1.0 12 Jan 2022

19ET004 **Appendix A** MTD V1.0 12 Jan 2022

19ET004 **Appendix B** Acoustic and EGG measures and justification V1.0 12 Jan 2022

19ET004 **Appendix C** Indirect Voice therapy Advice sheet V1.0 12 Jan 2022

19ET004 **Appendix D** CVT4MTD\_ Invitation to Patient on WL for treatment of MTD V1.0 12 Jan 2022

19ET004 **Appendix E** CVT4MDT Participant information sheet V2.0 21Mar 2022

19ET004 **Appendix F** CVT4MTD\_ Informed-Consent-Form V2.0 21 Mar 2022

19ET004 **Appendix G** CVT4MDT Patient & Public Involvement & Engagement survey sheet v0.3 V1.0  
12 Jan 2022

**Appendix H:** Schedule of Procedures (see below)

**Appendix I:** Amendment History (see below)

SHORT TITLE/ACRONYM: CVT4MTD

IRAS:306954

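### Acoustic and EGG reliability rests on Pearson's r alone, which cannot detect systematic disagreement between or within measurers

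*Combined protocol and SAP*

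**What the plan says.** The plan is in section 5 of the combined protocol and SAP, under Acoustic, EGG and MPT measures:

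- Amount of repeat work: "Measurement reliability for acoustic analyses will be calculated by reanalysis of 10% of the recordings".
- Choice of recordings: "The recordings chosen for reliability analysis will be randomly selected from the total number of recordings".
- Statistic: Pearson "correlations will be used to assess inter-measurer and intra-measurer reliability of the acoustic and EGG measurements".

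The plan text mentions no ICC, concordance coefficient, Bland-Altman analysis, within-subject SD or comparison of means between measurers for these variables. The one other use of Pearson's r, under Other Questionnaires, relates the discomfort scale to VHI and MPT and is not a reliability analysis. No target or threshold for r is given.

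The CAPE-V ratings, in the next part of section 5, are handled differently. Two scores agree if they lie within 21.5 mm, and "The probability of agreement will be calculated by totaling all pairs of scores that agree and dividing by the total number of score pairs". For the intra-rater check, "Twenty percent of the voice samples will be randomly selected to be repeated for each judge".

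Section 4.2 describes the source material as "voice recordings of continuous speech, phrases based on phonetically selected texts and sustained vowels" but does not say how many recordings each visit yields. Appendix B, listed in section 10.1 as "Acoustic and EGG measures and justification V1.0 12 Jan 2022", may say more, but its content was not available.

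**The concern.** A reader who sees a high reliability coefficient will take it to mean that two measurers, or one measurer on two occasions, obtain nearly the same value. Pearson's r does not show that. It shows only that the two sets of values lie close to some straight line, whatever its intercept and (positive) slope. A measurer who always reads higher, or whose readings are stretched relative to a colleague's, leaves r unchanged.

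This matters because the measures are used on their own scale: section 5 compares pre- and post-treatment values by paired t test and plots mean change with 95% confidence intervals. Secondary objective 4 (section 4.1) looks for the best measures of improvement, and objective 5 looks ahead to a larger RCT. Reliability evidence that cannot reveal a shift or a rescaling is a poor guide for that purpose. CAPE-V, in the same section, gets a criterion that does look at agreement.

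There is a smaller, conditional point. With few recordings, a 10% subset may be too small for any reliability coefficient to be informative.

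**Working it through.** The plan gives no expected reliability and no number of reanalysed recordings, so there is no figure of its own to reproduce. The check is of what the chosen statistic can detect.

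**1. Systematic difference without random error.** Let x be the first reading, with SD 1 across recordings, and y = a + s·x the second, with s > 0. Then r = 1 for every a and s. For two readings the absolute-agreement ICC is

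ICC = 2·cov(x, y) / [var(x) + var(y) + (mean difference)²].

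| Second reading | r | ICC |
|---|---|---|
| 0.5 SD higher | 1.00 | 2/(1 + 1 + 0.25) = 0.89 |
| 1 SD higher | 1.00 | 2/(1 + 1 + 1) = 0.67 |
| Same mean, spread doubled | 1.00 | 2·2/(1 + 4) = 0.80 |

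**2. The same with random error.** Assume each reading also has an error SD of 0.2, so each variance is 1 + 0.04 = 1.04 when s = 1. Then r = 1/1.04 = 0.96 whatever the offset b, and ICC = 2/(2.08 + b²).

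| Offset b (SD) | r | ICC | Bland-Altman limits, b ± 1.96·√0.08 |
|---|---|---|---|
| 0 | 0.96 | 2/2.08 = 0.96 | −0.55 to 0.55 |
| 0.5 | 0.96 | 2/2.33 = 0.86 | −0.05 to 1.05 |
| 1 | 0.96 | 2/3.08 = 0.65 | 0.45 to 1.55 |
| 2 | 0.96 | 2/6.08 = 0.33 | 1.45 to 2.55 |

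With no offset and a 1.5-fold stretch, var(y) = 2.25 + 0.04 = 2.29. Then r = 1.5/√(1.04·2.29) = 0.97 and ICC = 3/(1.04 + 2.29) = 0.90. A simulation of 200,000 pairs gave the same values.

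**3. Size of the subset (conditional).** Section 7.1 states: "Ten consecutive patients will be recruited". Section 5 sets two recording visits, t=0 and t=8. With k recordings per visit (k is not stated), the total is 10 × 2 × k.

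| k (assumed) | Recordings | 10% | 20% |
|---|---|---|---|
| 1 | 20 | 2 | 4 |
| 3 (one per task type) | 60 | 6 | 12 |
| 6 | 120 | 12 | 24 |
| 10 | 200 | 20 | 40 |

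With 2 recordings, r can only be +1 or −1 (or undefined). For larger n the Fisher-z 95% interval is tanh[atanh(r) ± 1.96/√(n − 3)]. At an observed r of 0.90, atanh(r) = 1.472:

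- n = 6: 1.472 ± 1.132, giving 0.33 to 0.99
- n = 12: 1.472 ± 0.653, giving 0.67 to 0.97
- n = 20: 1.472 ± 0.475, giving 0.76 to 0.96

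The F-based 95% interval for an absolute-agreement ICC of 0.90 without bias is 0.521 to 0.985 at n = 6 and 0.702 to 0.970 at n = 12. All these intervals treat recordings as independent. They come from only ten patients, so the true intervals may be wider.

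**The case against.** The strongest objection concerns the change scores. If one measurer analyses both of a patient's recordings, a constant offset b cancels: (post + b) − (pre + b) = post − pre. The offsets illustrated would then leave the treatment estimate as it was. That is correct, and it is why no bias in a treatment estimate is claimed. The cancellation needs the same measurer, without drift, at both time points, and the plan does not say who analyses the recordings. If the measurer changes, the difference becomes post + b − pre, that is, the true change plus b. A stretch by s multiplies the change by s and does not cancel.

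A second objection is that the section speaks of reliability rather than agreement, and that acoustic measures are less subjective than rating scales, so a different method from CAPE-V is a legitimate choice. The two methods need not match. But r is weak even as a consistency index, since it also misses the stretch. If software-derived values really carry little offset, an agreement analysis of the same readings would show that.

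Third, the offsets are hypothetical, no decision rule hangs on r, and these are secondary measures in a ten-patient proof-of-concept study. All true; this limits the importance of the point but does not remove it.

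Fourth, Appendix B could name a further statistic. That cannot be excluded. The SAP text itself still fixes Pearson's r and refers to no other method, so the two would need reconciling.

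Last, the subset-size point rests on an assumed number of recordings and largely disappears at ten per visit. That stands, and the conclusion does not depend on it.

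**Conclusion.** The concern holds. As written, the analysis cannot distinguish measurers who agree from measurers who differ by a constant or a scale factor. In the illustrations with random error, r stays at 0.96 while absolute agreement runs from 0.96 down to 0.33. That property of r is mathematical and needs no assumption about the data. The offsets, stretches and error SD are assumed, and nothing in the documents shows that such disagreement exists or is likely.

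The damage is limited to the evidence offered for the reliability of the secondary acoustic and EGG measures. The point should be corrected, but it does not threaten the trial's main result. That Pearson's r is the sole statistic is established for the plan text, with Appendix B unseen. Whether the 10% subset is also too small is undetermined until the number of recordings is stated.

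**What to change.** In section 5, replace Pearson's r with the following for each acoustic and EGG measure, separately for inter- and intra-measurer comparisons:

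- a two-way, absolute-agreement ICC with its 95% confidence interval;
- the Bland-Altman mean difference (bias) and limits of agreement. These are in the units of the measure and show the direction and size of any shift, which a single coefficient does not.

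State in the SAP how many recordings will be reanalysed, and check the wording against Appendix B. If the number is small, consider stratifying the random draw by task and enlarging it, for example to the 20% already used for CAPE-V. Reanalysing every session is not required.

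The change of statistic costs only SAP wording, since it uses paired readings already planned. The optional move from 10% to 20%, with separate inter- and intra-measurer repeats, would add (12 − 6) × 2 = 12 reanalyses at an assumed three recordings per visit, (4 − 2) × 2 = 4 at one, and (24 − 12) × 2 = 24 at six. No new patients, visits or recordings are needed.

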### **CAPE-V**

For the secondary outcome measure CAPE-V, three experienced judges will be asked to rate all voice samples using the first four dimensions (overall severity, roughness, breathiness, and strain; on 100-mm visual analog scales (VAS) (Kempster et al, 2009). The judges will be blinded to pre- and post-treatment status of the voice samples. The voice samples will be presented in random order. The rating forms will be scored, and then scores for each subject will be averaged across the three judges. Average scores will be used for group analyses. Interrater agreement will be assessed using procedures described by Kreiman and Gerratt (1998). Agreement equivalent to within 1 point on a 7-point Equal Appearing Interval (EAI) scale will be calculated for each possible pair of raters for each voice sample. On a 100-mm visual analog scale, scores that fall within 7.2 mm will be considered to be in exact agreement on a 7-point EAI, and scores that are within 21.5 mm (7.2 + 14.3 mm) will be considered to be within 1 scale value. Two scores will be considered to agree if they fall within  $\pm 21.5$  mm on the VAS (probability of chance agreement  $p = 0.39$ ). The probability of agreement will be calculated by totaling all pairs of scores that agree and dividing by the total number of score pairs. Twenty percent of the voice samples will be randomly selected to be repeated for each judge. Repeat ratings will be used to assess intra-rater agreement, using the same calculation. To test for differences in the four CAPE-V dimensions, a multivariate analysis of variance will be applied to the pre-treatment to post-treatment change ( $\Delta$ ). Paired-samples  $t$  tests will also be applied to pre-treatment to post-treatment changes for each of the four dimensions within each group. A multiple comparison adjustment will be made for the four comparisons using the Bonferroni multiple-comparison procedure. The confidence intervals will be similarly adjusted for four comparisons, so the reported 95% confidence interval (CI) will actually be a 98.75% CI, which is a Bonferroni-adjusted CI.

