### 7.2.1. Size of sample

As this is a proof-of-concept study the sample size of ten patients was selected arbitrarily to generate the necessary results for a power analysis for future studies.

SHORT TITLE/ACRONYM: CVT4MTD

IRAS:306954

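### Holm's step-down procedure could replace single-step Bonferroni for the four CAPE-V tests: same family-wise bound, never fewer rejections, and a gain of about 0 to 14 power points depending on effects the plan does not give

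*Combined protocol and SAP*

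**What the plan says.** The CAPE-V part of section 5 has three blinded judges rate "overall severity, roughness, breathiness, and strain", with scores averaged across judges. Paired t-tests "will also be applied to pre-treatment to post-treatment changes for each of the four dimensions within each group", and "a multivariate analysis of variance will be applied to the pre-treatment to post-treatment change". No rule says whether the multivariate test must be significant before the t-tests are read.

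For multiplicity the plan says "A multiple comparison adjustment will be made for the four comparisons using the Bonferroni multiple-comparison procedure". The intervals follow suit: "so the reported 95% confidence interval (CI) will actually be a 98.75% CI, which is a Bonferroni-adjusted CI".

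The part of section 5 on acoustic, EGG and MPT measures adds a rule about primary and secondary outcome analyses: "the alpha level for all t-test comparisons will also be assessed at .025". Neither part says how this level combines with the CAPE-V adjustment, or whether the tests are one- or two-sided.

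On size, section 7.2.1 says that "the sample size of ten patients was selected arbitrarily to generate the necessary results for a power analysis for future studies". No effect size, standard deviation, correlation or power is given for CAPE-V.

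**The concern.** Single-step Bonferroni holds every dimension to .05/4 = .0125, even after other dimensions have been declared changed. Holm orders the four p-values and compares them in turn with .05/4, .05/3, .05/2 and .05, stopping at the first failure. Its first step is the Bonferroni test, so it rejects everything Bonferroni rejects and sometimes more. Like Bonferroni, it needs no assumption about how the dimensions are related.

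With ten patients, power is scarce. The plan says it wants to control Type 1 error while keeping acceptable power, and its fourth secondary objective (section 4.1) is to find which measures best reflect improvement. Which CAPE-V dimensions are declared changed therefore has some interest, beyond whether any is. At stake is the number of truly changed dimensions that miss significance only because of the procedure chosen.

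**Working it through.** **The plan's own figure.** Four comparisons at family level .05 give .05/4 = .0125 per test and an interval of 1 − .0125 = 98.75%, as stated. The family-wise bound is 4 × .0125 = .05. With independent tests the error would be 1 − (1 − .0125)^4 = .0491.

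**Inputs.** From the documents: four dimensions, paired t-tests, ten patients, family level .05 (implied by the 98.75% interval). Assumed, because the documents are silent: two-sided tests, normal change scores, equal correlation between dimensions of 0 to 0.9, and d (mean change divided by the SD of the change) of 0.3 to 1.5. Power was found by simulation, with 30,000 or more trials per setting and a Monte Carlo error of about 0.3 points or less.

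**Error control.** Simulated family-wise error at correlation 0:

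| True effects | Bonferroni | Holm |
|---|---|---|
| none | .048 | .048 |
| one | .038 | .045 |
| three | .013 | .030 |

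Both stay at or below .05.

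**Power per dimension, all four effects equal, correlation 0.5** (gains are from unrounded values):

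| d | Bonferroni | Holm | Gain, points |
|---|---|---|---|
| 0.3 | 4.6% | 5.3% | 0.7 |
| 0.5 | 12.2% | 15.0% | 2.8 |
| 0.8 | 34.6% | 43.6% | 9.0 |
| 1.0 | 54.8% | 67.1% | 12.4 |
| 1.2 | 73.5% | 85.5% | 12.0 |
| 1.5 | 91.7% | 97.7% | 5.9 |

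At d = 1.0 the chance that all four dimensions are declared changed rises from about 22% to 50% (correlation 0.5) or from 29% to 55% (correlation 0.7).

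**Correlation.** At d = 1.0 the gain falls from about 14 points at correlation 0 to about 12 at 0.5 and 9 at 0.9. At d = 1.2 it falls from about 14 to 8. At d = 0.8 it is roughly flat at 8 to 9. It rises with correlation only at d of 0.5 or less, where it never exceeds 4 points.

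**Unequal effects.** With one dimension changing at d = 1.0 the gain on it is 0.1 to 0.2 points. With two it is about 3 (roughly 55% to 58%), and with three about 6 to 8. With graded effects (1.2/0.8/0.5/0.3 or 1.0/0.8/0.6/0.4) the gains run from about 0.5 to 9.

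**At least one rejection.** The two procedures agree exactly in every setting, because both test the smallest p-value at .0125.

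**Fewer completers.** With eight patients and correlation 0.5, the gains at d = 0.8, 1.0 and 1.2 are 6.3, 10.5 and 13.4 points.

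**The .025 rule.** Ten patients, correlation 0.5:

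| d | Family level .05 | Family level .025 | Family level .05, last step capped at .025 |
|---|---|---|---|
| 0.8 | 9.0 | 5.6 | 6.7 |
| 1.0 | 12.4 | 10.0 | 9.0 |
| 1.2 | 12.0 | 12.6 | 8.7 |

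The cap matters because Holm's last step at family level .05 is .05, twice the limit set for all t-tests. Bonferroni's .0125 is below .025 throughout.

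**The case against.** The strongest reply is that nothing here is wrong. Bonferroni is valid, CAPE-V is one of several secondary outcomes, and no stated decision depends on how many dimensions reach significance. Bonferroni also keeps tests and intervals in agreement: a dimension is significant exactly when its 98.75% interval excludes zero. Holm gives that up, since a dimension can pass a later step with a p-value above .0125. All of this stands. It makes the point optional and means that the relation between tests and intervals must be spelled out.

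A reader might infer that Bonferroni discards real improvements for no gain in error control. That goes too far. The nominal bound is the same, but Bonferroni's realised error is lower when some effects are real (.013 against .030 with three). The changes and their adjusted intervals are reported whichever procedure governs the tests.

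A reader might also infer that ratings of the same samples by the same judges are where a step-down procedure gains most. Shared samples and judges make correlation plausible, but they do not make the effects equal. For large equal effects the gain per dimension shrinks as correlation rises.

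**Conclusion.** Holm is a modest improvement available at almost no cost; the planned Bonferroni adjustment is not an error. Holm's family-wise bound and its never rejecting fewer dimensions follow from the procedure itself and need none of the assumptions above.

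The size of the gain does depend on them. Over d of 0.3 to 1.5 and correlation 0 to 0.9 it is about 0 to 14 points per dimension at ten patients. It reaches about 8 to 14 only if all four dimensions change by a similar large amount (d of 0.8 to 1.2). It is about 3 if two change at d = 1.0, near 0 if one does, and under 4 at d of 0.5 or less.

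It would be tempting to quote 9 to 12 points as the general gain. The documents give no CAPE-V effect size or correlation that would support a single figure, and the chance of finding at least one changed dimension does not improve at all.

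**What to change.** In the CAPE-V part of section 5, name the Holm step-down procedure in place of Bonferroni for the four significance decisions, and report Holm-adjusted p-values.

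State the CAPE-V family alpha and that the tests are two-sided, so that this part agrees with the .025 rule for all t-tests:

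- Family level .05: Holm steps .0125, .0167, .025 and .05, with 98.75% intervals. Say that the .025 rule does not cap the CAPE-V steps.
- Family level .025: Holm steps .00625, .0083, .0125 and .025, with intervals of 1 − .025/4 = 99.375%.

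Keep the Bonferroni-adjusted intervals as conservative simultaneous intervals. Add one sentence saying that decisions follow Holm and that a Holm-significant dimension may have an interval that includes zero.

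The cost is one changed phrase, a statement of alpha and a note, settled before the ratings are unblinded. No extra patients or data are needed. The price is the loss of exact agreement between tests and intervals.
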